### 8.5 **Procedure Assessments**

### 8.5.1 Subject Randomization

Subjects will be prospectively randomized. Randomization must occur prior to the start of CPB surgery, but only after the subject provides written informed consent and subject eligibility criteria is confirmed. Randomization should be performed within 5 days of start of the CPB surgery to minimize incidence of dropout prior to cardiac surgery and to allow adequate time for scheduling with the FCE. Subjects will be randomly assigned in a one to one (1:1) ratio to either the control arm (SOC) or treatment arm (SOC + CytoSorb® device). To ensure even distribution of subjects receiving treatment and control, with and without Hypothermic Circulatory Arrest (HCA) during procedure, the randomization will be stratified by study center and the intended use of HCA as a surgical technique during procedure.

Neither the investigational sites nor the Sponsor will have access to the randomization schedules, and subjects will not be told about their assignment prior to the surgery. A copy of the randomization assignment will be maintained in the subject's file. If the subject withdraws consent prior to the surgery, the reason for failure to treat as randomization will be recorded in the subject's study records. Safety data will not be collected for subjects who drop out prior to surgery.

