### **11.1 Analysis Populations**

Intent-to-Treat (ITT): All randomized patients.

Modified Intent-to-Treat (mITT): All randomized patients who meet all inclusion criteria through the completion of the surgical procedure. There are two mITT analysis sub-populations defined as follows:

- The primary sub-population includes all subjects enrolled and randomized to the treatment group who are undergoing valve replacement with another procedure (e.g., CABG, valve replacement) *without* Hypothermic Circulatory Arrest (HCA). This is the primary population for efficacy analyses.
- The secondary sub-population consists of all surgical subjects enrolled and randomized to the treatment group who are undergoing aortic reconstructions with or without other procedures (e.g., CABG, valve replacement) *with* HCA. This is a secondary population for efficacy analyses.

The primary analyses on the primary efficacy endpoint will be performed on these subpopulations. Subjects will be analyzed according to the treatment to which they were randomized.

Safety: Comprised of all roll-in and randomized subjects in whom treatment was attempted. Safety analysis will be performed on this population; it will also be performed separately on the above mITT populations. Patients will be summarized according to the actual treatment received.

Per Protocol (PP): Defined as the subset of patients in the mITT sub-population who had no major protocol violations. Efficacy analyses on the two PP sub-populations will be considered secondary. Patients will be analyzed by actual treatment received.

Roll in patients are not randomized and are only included in the safety population.

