### 11.1.2 Effectiveness evaluations:

The primary endpoint will be assessed in each modified intent-to-treat (mITT) population in step-wise fashion beginning with the primary sub-population. If a significant beneficial effect is met for CytoSorb over control at a one-sided overall 0.025 level of significance, then the study will be considered to be a primary endpoint statistical success on this subpopulation and testing will proceed to the secondary sub-population. Otherwise the study will be considered to have statistically failed the primary endpoint.

We have selected to use a modified intent-to-treat population (mITT) population to avoid the consequence of including patients that were excluded from the study after randomization due to administrative reasons.

Use of the mITT population as defined is not anticipated to result in bias or informative censoring of the data.

The primary endpoint (rank order presence and severity of AKI) will be compared between treatments with Wilcoxon Rank Sum test. Continuous endpoints will be assessed via ANCOVA with baseline value as covariate. Binary endpoints will be assessed via unconditional exact binomial test. The primary endpoint will be summarized by subgroup factors, e.g., those who receive IV contrast within 48 hours prior to surgery versus those who do not. Additionally, subgroup-by-treatment interaction may be tested via generalized ordered categorical model and/or for binary combinations of outcomes (e.g., presence / absence of any AKI, and/or severe AKI) by logistic regression. Details will be in the SAP.

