### 11.2 Statistical Power and Sample Size Determination

The REFRESH II study hypothesis is that, for patients at increased risk for AKI based upon use of the Cleveland Clinic Score for stratification of the risk of cardiac surgery associated AKI (CSA-AKI), the intra-operative usage of the CytoSorb device in addition to the standard of care in a bypass circuit during cardiopulmonary bypass will decrease the overall incidence and/or proportion of acute kidney injury (AKI) by stage as defined by the Kidney Disease Improving Global Outcomes (KDIGO) clinical practice guideline definition of acute kidney injury. The AKI Stage is scored as 0, 1, 2 or 3. AKI Stage of 0 indicates no AKI, and AKI stages 1, 2 and 3 indicate mild, moderate, and severe AKI, respectively. Success will be defined by demonstrating a shift in distribution toward overall less severe AKI or fewer incidences of AKI in the CytoSorb population.

The distribution of AKI Stage (0, 1, 2, 3) expected in the control group was estimated from prior data. Sample trial outcomes for which power was computed are summarized in **Error! Reference s ource not found.** below for total N=267 patients in the primary analysis subgroup ("without HCA", randomized 1:1). The proportion of "without HCA" patients will be at least 2/3 of the total sample size 400. 420 patients will be enrolled to account for an expected 5% premature withdrawal rate. Power was computed for comparing binomial proportions of patients with AKI Stage 1, 2, or 3 (or i.e., any AKI); proportions with AKI Stage 2 or 3; and for an ordered categorical rank test comparing the distribution of AKI Stages 0, 1, 2, 3 between treatments. Since it is uncertain whether CytoSorb will lower the overall AKI rate or that of Stages 2 and 3, the ordered categorical test will be primary, i.e., the primary null and alternative hypotheses are

- H0:  $\pi 00 = \pi 01$ ,  $\pi 10 = \pi 11$ ,  $\pi 20 = \pi 21$ ,  $\pi 30 = \pi 31$
- H1:  $\{\pi 30 \ge \pi 31 \text{ and/or } (\pi 20 + \pi 30) \ge (\pi 21 + \pi 31) \text{ and/or } (\pi 10 + \pi 20 + \pi 30) \ge (\pi 11 + \pi 21 + \pi 31)\}$  AND one or more of the above is strictly ">"

where  $\pi i0$  is the proportion of control patients in AKI level i (i=0, 1, 2 and 3) and where  $\pi i1$  is the proportion of CytoSorb patients in level i. Note that level i=0 is no AKI. The test of the null

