To ensure proper training and competence related to integration of the investigational study device at all sites a roll-in approach was employed where the first two enrolled subjects from each site were used for training. All subjects enrolled as roll-in cases were treated with the CytoSorb[®] device and followed per protocol.

The initial design included interim analyses with the potential of (NON-BINDING) early stopping for an efficacy or futility conclusion, and an option to increase sample size (SSR, i.e., Sample Size Reestimation).

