4.2 Randomization

Subjects will be randomized prior to the start of CPB surgery (within 5 business days prior to and including day of procedure), but only after the subject provides written informed consent and subject eligibility criteria is confirmed. Randomization will be stratified by study center and intended use of HCA as a surgical technique during the procedure, with a 1:1 allocation ratio (SoC+CytoSorb[®]:SoC alone). Randomized treatment will be assigned from the electronic database.

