6.7.1.1 Primary Analysis

AKI severity (stage 0, 1, 2, 3) based on creatinine measured at CPB, 24-hours post-CPB, and 48-hours post-CPB will be summarized using descriptive statistics. Summaries will be provided for the ITT and Roll-ins. Data will be displayed by treatment group and overall, with Roll-ins presented in parallel. AKI stage is based on the 'worst' criteria being met and subjects included in each severity level will be mutually exclusive across levels.

The number and proportion of subjects will be given for the following severity breakdowns:

CytoSorbents

| Statistical Analysis Plan | | Pag | ge 13 of 19 |
|---------------------------|--|-----|-------------|
| Sponsor | Study | | Version |
| CytoSorbents | Ents CytoSorb [®] REduction of FREe Hemoglobin/Acute Kidney Injury (AKI) during Cardiac Surgery | | 1.0 |

- Stage 0 (no AKI)
- Stage 1 (mild AKI)
 - \circ Serum creatinine increase of 1.5-1.9 times baseline, or
 - Serum creatinine increase of ≥0.3mg/dL over baseline, or
 - urine output < 0.5 mL/kg/h for 6 h
- Stage 2 (moderate AKI)
 - o Serum creatinine increase of 2.0-2.9 times baseline, or
 - urine output < 0.5 mL/kg/h for ≥ 12 h
- Stage 3 (severe AKI)
 - Serum creatinine ≥3 times baseline, or
 - Serum creatinine increase to ≥4.0mg/dL, or
 - Initiation of renal replacement therapy, or
 - urine output < 0.3 mL/kg/h for ≥ 24 h, or
 - anuria for ≥ 12 h
- Stage 1, 2, or 3
- Not reported

Comparisons between SoC and SoC+CytoSorb[®] will be made using Fisher's exact tests. Statistical comparisons will be done for the ITT population only.

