6.9 Subgroup Analyses

Primary efficacy will be summarized for the following subgroups: HCA (Y/N), IV contrast within 48hrs prior to surgery (Y/N), biological sex (M/F), age (Age<65, Age \geq 65), baseline diabetes mellitus (Y/N), baseline heart failure (Y/N), and baseline hypertension (Y/N).

The outcome of interest will be AKI severity of 0 versus AKI severity of 1/2/3 at 48 hours. Logistic regression will be used to determine the odds ratio for SoC+ CytoSorb versus SoC within each subgroup. The odds ratio and associated 95% confidence intervals for each subgroup will be presented in a forest plot. The analysis will be repeated but with the outcome being AKI severity of 0 or 1 versus AKI severity of 2 or 3.

Analyses will be performed in the ITT population (excluding Roll-ins). These analyses are intended to demonstrate consistency of results across subgroups.

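### SAP 6.7.1.1 compares the arms in pooled ITT with unstratified Fisher's exact tests, although intended HCA is a randomisation stratum; no overall HCA-adjusted comparison is planned

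*SAP*

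**What the plan says.** SAP 4.2 states: "Randomization will be stratified by study center and intended use of HCA as a surgical technique during the procedure, with a 1:1 allocation ratio". Protocol 8.5.1 agrees: "the randomization will be stratified by study center and the intended use of HCA as a surgical technique during procedure".

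SAP 6.7.1.1 compares SoC with SoC+CytoSorb on AKI stage by Fisher's exact tests and adds: "Statistical comparisons will be done for the ITT population only". It names no stratum or covariate, so the tests are read here as unstratified. It also does not say whether one table of arm by four stages is meant, or several two-by-two tables. SAP 6.2 defines ITT as every randomised patient and lists no other efficacy population, so patients with and without HCA are pooled.

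The protocol kept these groups apart. Section 11.1 defines a primary sub-population without HCA and a secondary one with HCA, and says: "The primary analyses on the primary efficacy endpoint will be performed on these subpopulations". Section 11.1.2 adds: "The primary endpoint will be assessed in each modified intent-to-treat (mITT) population in step-wise fashion beginning with the primary sub-population". Testing moves to the second group only after success in the first.

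In the SAP's analyses HCA returns only in section 6.9, as one of seven subgroup factors: "Primary efficacy will be summarized for the following subgroups: HCA (Y/N"). That section gives a separate treatment odds ratio within each level, at two binary cut-points (stage 0 against 1 to 3, and 0 or 1 against 2 or 3).

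SAP 4.1 reports that the study stopped before any interim analysis, with 151 of 420 planned subjects enrolled, roll-ins included.

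**The concern.** A factor used to stratify randomisation is normally carried into the primary comparison. Balancing allocation on a prognostic factor reduces the true variance of the treatment difference. An analysis that ignores the factor uses too large a variance, so it is conservative and can lose power.

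Interpretation matters too. The protocol thought HCA important enough to stratify on and to define its primary population. The report will pool the two surgical groups, and no overall result will account for the factor that separates them. The subgroup odds ratios do not fill the gap: they give no combined estimate and split a small trial further. SAP 6.9 also does not say whether HCA there means intended or actual use. Protocol 8.4 allows the procedure to change on the day of surgery, so the two can differ, and only intended use was the stratum.

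**Working it through.** **1. Planning inputs.** Protocol Table 5 gives stages 0/1/2/3 as 24/47/26/3% for control, 36/53/10/1% for CytoSorb in Example 1 and 44/40/14/2% in Example 2. To confirm these, its binary powers were recomputed with n = 267/2 = 133.5 per arm and one-sided 0.025:

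power = Φ[(p1 − p2 − 1.96·SE0)/SE1], where SE0² = 2p̄(1 − p̄)/n and SE1² = [p1(1 − p1) + p2(1 − p2)]/n.

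For any AKI in Example 1 (0.76 against 0.64), SE0 = 0.0561, SE1 = 0.0556, and power = Φ(0.0101/0.0556) = 0.572. The four results are 0.572, 0.961, 0.936 and 0.723, against 0.57, 0.96, 0.94 and 0.72 stated. A simulated Wilcoxon test gives 0.933 and 0.957, consistent with the stated power of over 90%.

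**2. Number randomised.** This is not given. SAP section 4 says "the first two enrolled subjects from each site were used for training". Assuming two roll-ins at every site: 151 − 2×40 = 71, 151 − 2×20 = 111, 151 − 2×10 = 131. Protocol Table 1 counts a consented patient as enrolled, so the true number could be lower.

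**3. HCA share and effect.** Protocol 11.2 says of the without-HCA group that its "patients will be at least 2/3 of the total sample size 400", so the planned maximum HCA share is one third. The HCA effect on AKI is not given. Cumulative odds ratios (OR) of 1, 2 and 4 were assumed, applied in both arms. OR 4 is strong: stage 2/3 AKI in controls goes from 29% (odds 0.408) to 62% (odds 1.634).

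**4. Tests.** In stratum h, W_h is the treatment-arm rank sum, with null mean E_h and tie-corrected variance V_h. The van Elteren statistic is Z = Σ w_h(W_h − E_h)/√(Σ w_h²V_h), with w_h = 1/(N_h + 1). The pooled Wilcoxon test is the same with one stratum. Comparing these two isolates stratification from the separate matter of using stage order.

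**5. Power.** Two-sided 0.05 (SAP 6.1.4), 12,000 trials per cell, equal centres, blocks of 4 within centre by HCA, one third HCA. Entries are pooled Wilcoxon / van Elteren.

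| N (sites) | Example | OR 1 | OR 2 | OR 4 |
|---|---|---|---|---|
| 71 (40) | 1 | 0.422 / 0.412 | 0.452 / 0.459 | 0.460 / 0.491 |
| 71 (40) | 2 | 0.460 / 0.456 | 0.440 / 0.445 | 0.386 / 0.426 |
| 111 (20) | 1 | 0.603 / 0.602 | 0.647 / 0.658 | 0.657 / 0.698 |
| 111 (20) | 2 | 0.661 / 0.659 | 0.624 / 0.634 | 0.564 / 0.612 |
| 131 (10) | 1 | 0.684 / 0.682 | 0.719 / 0.730 | 0.730 / 0.769 |
| 131 (10) | 2 | 0.732 / 0.730 | 0.707 / 0.716 | 0.640 / 0.687 |

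Gains in points, from unrounded values: −0.9 to −0.1 at OR 1, +0.5 to +1.1 at OR 2, +3.1 to +4.8 at OR 4 (Monte Carlo SE 0.1 to 0.3). With 20% HCA: −0.3 to +0.9 at OR 2 and +1.7 to +3.6 at OR 4. With 10%: −0.7 to +0.4 and +0.3 to +1.8. A test that ignores stage order (Cochran-Mantel-Haenszel general association, unstratified against stratified, one third HCA) gains about the same: −0.5 to 0, +0.3 to +1.3, and +2.6 to +5.2.

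**6. Type I error at OR 4**, for N = 71, 111, 131 in one run of 12,000: Fisher on the 2×4 table 0.045, 0.044, 0.042; pooled Wilcoxon 0.049, 0.042, 0.038; van Elteren 0.049, 0.048, 0.050.

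**7. Binary cross-check.** Pooled chi-square was compared with Cochran-Mantel-Haenszel (CMH) by HCA, one third HCA, N = 71, 111, 151. With equal risk in the strata the power difference is about 0. With control stage 2/3 risk of 0.29 without HCA and 0.70 with HCA, power is 0.236, 0.348, 0.465 pooled and 0.282, 0.410, 0.529 stratified. Type I error is then 0.029, 0.029, 0.035 pooled and 0.050, 0.048, 0.048 stratified. Fisher on two-by-two tables ran at 0.015 to 0.032 over all scenarios. With equal stratum risks it was already at 0.025 to 0.032, so much of that conservatism belongs to the exact test and not to ignoring HCA.

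**8. What stratifying does not do.** Suppose only non-HCA patients benefit (Example 1, OR 2). For N = 71, 111, 131, power is 0.211, 0.304, 0.349 with pooled Wilcoxon; 0.212, 0.316, 0.362 with van Elteren; and 0.293, 0.439, 0.507 with non-HCA patients tested alone.

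**The case against.** The strongest reply is that this is a preference and not an error. The pooled test is valid. Stratifying costs a little power if HCA is not prognostic, and gains of 3 to 5 points need an HCA effect that nothing in the documents supports. All of that stands and limits the point to an optional improvement.

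The main power comparison uses Wilcoxon tests, and the SAP specifies Fisher. This is fair, and deliberate: setting van Elteren against Fisher on one 2×4 table would show about 3 to 15 points, but that gain comes from using stage order and is not claimed here.

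A van Elteren test still pools the two groups and does little if only non-HCA patients benefit. Step 8 confirms this.

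Centre is also a stratum and is left out of the proposed test. True, but 71 patients in 80 centre-by-HCA cells, 111 in 40 or 131 in 20 is about 1 to 7 per cell, too sparse to stratify the test on.

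The protocol's own Wilcoxon test was unstratified, and its sub-populations follow the surgery undergone, not the surgery intended. Both are true. However, that test was applied within HCA-defined groups, so HCA was handled by design. The proposal uses HCA as randomised and does not claim to recreate those populations. The protocol called the primary sub-population intended, to be confirmed at the interim analysis (6.3.2). That analysis never took place, so the confirmation gives no reason for pooling.

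Finally, the SAP discloses that its analyses may differ from the protocol. Disclosure does not explain why the stratum was left out.

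**Conclusion.** The concern holds as an improvement to consider. No overall comparison in the SAP accounts for intended HCA. The planned test does not inflate type I error; on the 2×4 reading it is mildly conservative if HCA is strongly prognostic. The effect of stratification on power runs from about a 1-point loss to a 1-point gain up to an assumed HCA odds ratio of 2, and reaches about 3 to 5 points at an odds ratio of 4 with one third HCA patients. These sizes rest on assumed values for the HCA effect, the HCA share, the number randomised and the block size, and on the Table 5 distributions. The gain is in efficiency and interpretation; an invalid test is not being corrected. Confidence is medium.

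**What to change.** In SAP 6.7.1.1:

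- Compare AKI stage 0 to 3 between the arms with a Wilcoxon test stratified by intended HCA as randomised (van Elteren). Do not stratify the test by centre.
- Show the stage table by arm within each intended-HCA stratum.
- State that this overall comparison does not replace the protocol's without-HCA primary analysis.
- Optionally, add a supporting proportional-odds model with treatment and intended HCA, and check proportionality. The cumulative odds ratios implied by Table 5 are not constant: 1.78, 3.30, 3.06 in Example 1 and 2.49, 2.14, 1.52 in Example 2. The first is (0.76/0.24)/(0.64/0.36) = 1.78.

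The cost is SAP wording only. Intended HCA is already recorded for randomisation, and SAP section 7 provides for an amended SAP before the analysis. If HCA turns out not to be prognostic, the power cost in the one-third-HCA runs was 0.1 to 0.9 points, largest with 71 patients over 40 sites.

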4.3 Blinding

See Section 3.6 of the CIP for additional details on Maintaining the Study Blind and Unblinding Procedures.

5 Sample Size Determination

The REFRESH II study hypothesis is that, for patients at increased risk for AKI based upon use of the Cleveland Clinic Score for stratification of the risk of cardiac surgery associated AKI (CSA-AKI), the intraoperative usage of the CytoSorb^{*} device in addition to the standard of care in a bypass circuit during cardiopulmonary bypass will decrease the overall incidence and/or proportion of acute kidney injury (AKI) by stage as defined by the Kidney Disease Improving Global Outcomes (KDIGO) clinical practice guideline definition of acute kidney injury. The AKI Stage is scored as 0, 1, 2 or 3. AKI Stage of 0 indicates no AKI, and AKI stages 1, 2 and 3 indicate mild, moderate, and severe AKI, respectively. Success will be defined by demonstrating a shift in distribution toward overall less severe AKI or fewer incidences of AKI in the CytoSorb^{*} population. For full explanation of sample size determination, refer to 2017-001, Version F section 11.2.

6 Statistical Analyses

| Statistical Analysis Plan | | Pa | ge 10 of 19 |
|---------------------------|--|----|-------------|
| Sponsor | Study | L | Version |
| CytoSorbents | CYTOSORB [®] REDUCTION OF FREE HEMOGLOBIN/ACUTE KIDNEY INJURY (AKI) DURING CARDIAC SURGERY | | 1.0 |

6.1 General Considerations

Except where otherwise specified, the following general principles apply to the planned statistical analyses. All statistical analysis will be conducted using SAS version 9.4 or later (SAS Institute Inc., Cary, NC) and/or the R software language.

6.1.1 Descriptive Statistics

Tabulations will be produced for appropriate demographic, baseline, efficacy, safety, and other parameters by treatment group and overall, with Roll-in subjects presented in parallel unless specified otherwise.

Continuous data will be summarized with mean, standard deviation, median, interquartile range, minimum, and maximum. Categorical variables will be summarized with frequency counts and percentages.

6.1.2 Study Day

Study day 0 is the date of the index procedure. Day in study will be calculated relative to the index procedure as follows:

```
Study Day = Assessment Date – Index Procedure Date
```

For each subject, duration in study will be based on last study contact date which is the latest date of all follow-up visits, assessments, adverse event onset or resolution, and study exit including date of death.

Duration variables will be calculated as follows:

```
Duration Days = End Date – Start Date
```

6.1.3 Visit Windows

Unless otherwise specified, visit based assessments will be analyzed for each analysis time point according to the nominal visit entered in the Case Report Form (CRF) regardless of if it is out of window.

6.1.4 Statistical Significance

Unless otherwise specified, hypothesis testing will be performed at the two-sided 0.05 significance level. P-values will be rounded to three decimal places. If a p-value is less than 0.001 it will be reported as "<0.001". If a p-value is greater than 0.999, it will be reported as ">0.999".

6.2 Analysis Populations

The following subject populations will be evaluated and used for presentation and analysis of the data:

| Statistical Analysis Plan | | Pa | ge 11 of 19 |
|---------------------------|---|----|-------------|
| Sponsor | Study | | Version |
| CytoSorbents | orbents CytoSorb [®] REduction of FREe Hemoglobin/Acute Kidney Injury (AKI) during Cardiac Surgery | | 1.0 |

• Intent-to-Treat (ITT): All randomized patients.

Safety (SAF): Comprised of all roll-in and randomized subjects in whom treatment was attempted. Safety analysis will be performed on this population. Patients will be summarized according to the actual treatment received, with Roll-in subjects presented in parallel.

